7.3.7. Sensitivity Analyses

To assess the robustness of the primary analysis, the following sensitivity analyses of the primary endpoint will be conducted at Week 24/EOT.

7.3.7.1. Sensitivity Analysis 1

To assess the potential impact of unvalidated feminine product use, the primary endpoint will be analyzed as sensitivity analysis in a similar fashion to the primary analysis using the Week 24/EOT validated MBL volume (obtained from the validated or validated-but-unauthorized feminine products only and excluding unvalidated products).

7.3.7.2. Sensitivity Analysis 2

To assess the potential impact of missing data due to inadequate collection of feminine products, the primary endpoint will be analyzed with a sensitivity analysis using the missing data handling rules as described in [Table 8](#) below where the observed MBL volume will be used to assess the responder status at Week 24/EOT when feminine product collection was incomplete. These rules differ from those used in the primary analysis in that no imputation will be implemented for patients with < 100% feminine product compliance and the reported MBL volume both < 80 mL and a $\geq 50\%$ reduction from Baseline as highlighted in [Table 8](#).

Table 8: Derivation of Responder Status at Week 24/EOT and Missing Data Handling Rules – for Sensitivity Analysis

Treatment Exposure	FP Collection (FPRR)	Observed MBL Volume	Reason for No FP Collection	Responder Status
< 4 weeks	N/A	N/A	N/A	Imputed as non-responder
\geq 4 weeks	100% FP Compliance	N/A	N/A	Based on the observed MBL volume
	< 100% FP Compliance	MBL volume \geq 80mL or $<$ 50% reduction from Baseline	N/A	Imputed as non-responder based on the observed MBL volume
		MBL volume $<$ 80mL and \geq 50% reduction from Baseline	N/A	Based on the observed MBL volume
No FP Collection	N/A	Reported “Amenorrhea”	Reported “Amenorrhea”	Imputed as responder
			Reported “Spotting or negligible bleeding” and confirmed by eDiary ^a	Imputed as responder
		Reported “Spotting or negligible bleeding” although not confirmed by eDiary or any other reason, had at least 8 weeks of MBL volume data	Based on the imputed MBL volume	
			The entries in the eDiary did not verify “Spotting or negligible bleeding” or any other reason and if had $<$ 8 weeks of MBL volume data	Imputed as non-responders

Abbreviations: eDiary, electronic diary; FP, feminine product; EOT, end of treatment; MBL, menstrual blood loss; N/A, not available.

^a Defined as those patients who meet the following criteria: eDiary entry rate $>$ 70% and no more than 3 consecutive days and no more than 5 days of bleeding/spotting and use of feminine product reported on the eDiary over the Week 24/EOT visit window (see Table 5).

7.3.7.3. Sensitivity Analysis 3

To assess the potential impact of early discontinuation on the primary endpoint, the primary endpoint will be analyzed with a sensitivity analysis defining the patients' responder status as follows:

- Patients who discontinued study drug during the first 4 weeks for any reason or who discontinued study drug between Week 4 and Week 12 due to an adverse event, surgery or other intervention for heavy menstrual bleeding, reported lack of efficacy, or bleeding complaints will be considered as non-responders;
- All other patients will have their responder status defined using data from the Week 24/EOT assessment period using the last observation carried forward method.

7.3.7.4. Sensitivity Analysis 4

To assess the potential impact of the length and full exposure of the treatment, the primary endpoint will be analyzed for the Completers population as a sensitivity analysis. The Completers population is defined as patients in the mITT population who completed 24 weeks of study treatment.

7.3.7.5. Sensitivity Analysis 5

The primary endpoint will be analyzed on the Per-Protocol population as a sensitivity analysis, using the methods specified for the primary analysis (see definition of Per-Protocol population in Section 4.2.2).

7.3.7.6. Sensitivity Analysis 6

As a sensitivity analysis to the primary analysis using the mixed-effects model for imputing missing MBL volumes at Week 24/EOT, multiple imputation approach will be implemented as described below.

A multiple imputation method (Rubin, 1987; von Hippel, 2018) will be used to impute missing or partially missing MBL volume identified by the missing data handling rules (see [Table 7](#) and [Table 8](#)) at Week 24/EOT as described in the following 5 steps. In this method, an arbitrary missing pattern will be assumed using Markov Chain Monte Carlo imputation to generate a monotone missing pattern for the observed longitudinal MBL volume values (including 0 mL if the patient has amenorrhea). Imputation will be performed separately by randomized treatment group (Sullivan, 2018), given the distinct bleeding patterns among the three treatment groups.

Normalizing transformations will be applied to the statistics estimated from each imputed dataset before the Rubin's combination rules can be applied (Ratitch, 2013). This combined estimation and statistical test will account for the additional variability due to imputation to provide a robust assessment of the treatment effect.

- Step 1: Identifying patients with missing or incomplete MBL volume from the longitudinal MBL volume dataset as collected.
- Step 2: Generating a monotone missing pattern using the Markov Chain Monte Carlo technique by imputing missing MBL volume measurements that are between non-missing results.

Step 3: Imputing the remaining missing values $m = 100$ times using a regression model; therefore, generating 100 complete longitudinal MBL volume datasets.

Note: if a patient missed Week 8 and prematurely discontinued study drug (eg, at Week 20) and MBL volume at Week 20 is missing or partially missing, MBL volume will be imputed for intermittent missing data at Week 8, Week 20 (EOT), and Week 24 due to discontinuation.

Step 4: Performing the same CMH test pre-specified for the primary endpoint analysis and estimating the responder rates for each arm using each of the 100 datasets based upon the MBL volume at Week 24/EOT.

Note: in the example above, the imputed MBL volume at Week 20 (EOT) will be used in the analysis, although MBL volume is imputed at Week 24.

Step 5: Combining the results from the 100 complete datasets to make inferences about the treatment effect on the responder rate.

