7.3.4. Definition of Responder at Week 24/EOT

A responder at Week 24/EOT is defined as a patient who satisfies both the following:

- Had MBL volume of < 80 mL at Week 24/EOT;
- Had at least a 50% reduction from Baseline in MBL volume at Week 24/EOT.

The reduction from Baseline in MBL volume at Week 24/EOT will be calculated as the absolute change at Week 24/EOT in MBL volume from the Baseline MBL volume divided by the Baseline MBL volume.

Responder status at Week 24/EOT will be assessed based on the reported MBL volume at Week 24/EOT, in conjunction with treatment duration, compliance with feminine product collection, and compliance with eDiary entry over the same visit window (see Section [7.3.5](#) for details).

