7.3.5. Derivation of Responder Status at Week 24/EOT and Missing Data Handling Rules

For the evaluation of primary endpoint, missing data handling rules will be implemented for deriving responder status at Week 24/EOT as described below. The following elements will be checked: duration of treatment exposure; compliance with feminine product collection against the eDiary, as measured by FP RR; compliance with eDiary entry, defined as the proportion of eDiary entry days over the length (days) of FP collection interval for Week 24/EOT visit; and reasons for no FP collection (as displayed in [Table 7](#)).

Patients with < 4 weeks of treatment who withdraw from the study prematurely due to lack of efficacy or withdraw from the study prematurely to undergo surgical intervention for uterine fibroids will be considered as non-responders.

All other patients will have their responder status determined as follows:

- For patients with a FP RR of 100%, responder status will be determined based on the observed MBL volume;
- For patients who had incomplete feminine product collection, with a FP RR of < 100%, responder status will be derived based on either imputed or observed MBL volume;
 - Those with an MBL volume \geq 80 mL or < 50% reduction from Baseline will be considered as non-responders;
 - Those with an MBL volume < 80 mL and \geq 50% reduction from Baseline will be imputed for partial or complete missing MBL volume (see Section [7.3.6](#) for details).
- For patients who did not return a feminine product collection, responder status will be determined depending on the reason reported on the Feminine Product Collection eCRF:
 - If the reason is reported as Amenorrhea, the last 35 days of treatment will be used to derive responder status:
 - If the Week 24/EOT interval was 35 days, then she will be considered as a responder;
 - If the Week 24/EOT interval was <35 days, the following supportive information will be used to derive responder status:
 - If a patient reported amenorrhea at the visit prior to Week 24/EOT, she will be defined as a responder;
 - If a patient did not report amenorrhea at the visit prior to Week 24/EOT, eDiary data from the prior visit interval will be reviewed to confirm whether the patient was amenorrheic for a total of 35 days.
 - If the eDiary from the previous interval confirms amenorrhea, then the patient will be considered as a responder;

- Otherwise, MBL volume will be imputed.

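### With the other imputations unchanged, Sensitivity Analysis 2 can only keep or raise each arm's responder rate, so it cannot show whether incomplete product collection inflated the relugolix rate

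*SAP*

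**What the plan says.** SAP section 7.3.4 sets two conditions for a responder: "Had MBL volume of < 80 mL at Week 24/EOT" and "Had at least a 50% reduction from Baseline in MBL volume at Week 24/EOT".

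Section 7.3.3 defines the FPRR as the days with returned product divided by the eDiary days with bleeding and product use. A value below 100% means that product from at least one reported day is missing.

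For women with FPRR < 100%, section 7.3.5 and Table 7 (primary analysis) make two cases:
- If the measured volume fails either criterion, the woman is a non-responder.
- If it meets both, her volume "will be imputed for partial or complete missing MBL volume" and her status follows the imputed value.

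Section 7.3.7.2 gives the aim of Sensitivity Analysis 2: "To assess the potential impact of missing data due to inadequate collection of feminine products". It provides that "the observed MBL volume will be used to assess the responder status at Week 24/EOT when feminine product collection was incomplete". Its rules depart from the primary in one respect: "no imputation will be implemented for patients with < 100% feminine product compliance and the reported MBL volume both < 80 mL" and the reduction is at least 50%. Table 8 bases the status of these women on the observed volume. The neighbouring row is unchanged: "Imputed as non-responder based on the observed MBL volume". Amendment 1 and the earlier SAP version carry the same text.

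**The concern.** The Table 8 entry reads like an assessment but has one possible result. A woman enters the row by meeting the two criteria that define response, and is then judged by the same volume against the same criteria.

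The risk in incomplete collection is that the missing products held blood. A partly collected volume is a lower bound on the true loss, and taking it at face value counts the uncollected blood as 0 mL. For an arm's responder rate that is the most favourable assumption available, and for these women it is more lenient than the primary imputation. A reader of the study report could take agreement between Sensitivity Analysis 2 and the primary result as evidence that poor collection did not inflate the relugolix responder rate. The analysis cannot supply that evidence.

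**Working it through.** **Plan figures.** The SAP gives no figure for this row. The only stated figure for the endpoint is power of at least 99% (section 2.2.1), which reproduces: 130 × 0.8 = 104 evaluable per arm, 55% versus 25%, two-sided 0.05, chi-squared test, power 99.5%. It is not in dispute.

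**Step 1: the rules side by side, FPRR < 100%.**

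| Measured volume | Primary (Table 7) | Sensitivity Analysis 2 (Table 8) |
|---|---|---|
| ≥ 80 mL or < 50% reduction | non-responder | non-responder |
| < 80 mL and ≥ 50% reduction | by imputed volume, either status | by observed volume, always responder |

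Both rules were enumerated over Baseline 80 to 600 mL, observed 0 to 300 mL and imputed −100 to 400 mL, giving 808,303 combinations. None was a responder in the primary and a non-responder in Sensitivity Analysis 2; 133,062 went the other way. The changed row held no non-responders under Table 8.

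**Step 2: the other listed analyses.**
- Analysis 1 drops unvalidated products and otherwise follows the primary.
- Analysis 3 penalises certain early discontinuations, and uses last observation carried forward for everyone else.
- Analysis 4 restricts to completers and states no different responder rule.
- Analysis 5 applies the primary methods to the Per-Protocol population.
- Analysis 6 re-imputes missing and partially missing volumes within arm.

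The primary and Analysis 6 may make some of these women non-responders. None makes all of them so.

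**Step 3: what the row can do.** Let fA and fC be the row's share of each arm, and pA and pC the fraction of it scored as response. The row adds pA·fA to the relugolix rate, pC·fC to the placebo rate and pA·fA − pC·fC to the unadjusted difference. Each p runs from 0 to 1, so the relugolix rate spans fA and the difference runs from −fC to +fA, a span of fA + fC. Sensitivity Analysis 2 fixes pA = pC = 1.

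The shares below are assumptions, shown in both directions. With 130 women, 12% is 15.6 and 8% is 10.4. Entries are points added to the difference.

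| fA, fC | All responders (Analysis 2) | All non-responders | Relugolix non-responders, placebo responders | Reverse | Span |
|---|---|---|---|---|---|
| 12%, 8% | +4 | 0 | −8 | +12 | 20 |
| 8%, 12% | −4 | 0 | −12 | +8 | 20 |

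Scoring both arms as non-responders does not bound the difference from below. In the second line it gives a larger difference than Sensitivity Analysis 2.

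**Step 4: counts near the planned rates (assumed).** Start from 72/130 versus 33/130, which is 55.4% versus 25.4%, a difference of 30.0 points.
- Sensitivity Analysis 2 turns 10 relugolix women and no placebo women into responders: 82/130 = 63.1% versus 25.4%, difference 37.7.
- It turns no relugolix women and 10 placebo women into responders: 55.4% versus 43/130 = 33.1%, difference 22.3.
- Ten primary relugolix responders in the row are instead scored as non-responders, placebo unchanged: 62/130 = 47.7%, difference 22.3.
- The same, with 10 placebo women also becoming responders: (62 − 43)/130 = 14.6 points.

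**The case against.** The strongest reply is that robustness concerns the treatment difference and its Cochran-Mantel-Haenszel test, and Sensitivity Analysis 2 applies its rule to both arms. The primary imputation model in section 7.3.6 includes treatment and visit by treatment, so placebo women may be imputed as non-responders and relugolix women as responders. Removing the imputation could then raise mainly the placebo rate and shrink the difference. This stands, and Step 4 shows it. The analysis has a legitimate use as a test of dependence on the imputation.

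It also stands that the primary analysis does not accept low partial volumes at face value, and that Analysis 6 imputes them again by a different method.

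On size, women who return nothing because of amenorrhea have their FPRR set to 100% (section 7.3.3) and cannot enter this row. If amenorrhea is commoner on relugolix, the row could be the larger one on placebo. A range that assumes fA > fC is therefore unsupported.

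Finally, FPRR < 100% includes a woman who missed a single product-day, so scoring the whole row as non-response is extreme. That is a caution for interpretation. It does not remove the gap: the stated aim is the effect of inadequate collection, and for the relugolix rate only the lenient end is calculated.

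**Conclusion.** The point holds for the arm rates. Every woman whose handling changes is a responder by definition, so Sensitivity Analysis 2 cannot lower either arm's rate. This assumes that the imputations in the other rows are the same in both analyses; the SAP does not say whether partial volumes enter the mixed model. The size is fA for the relugolix rate and up to fA + fC for the difference, both unknown from the SAP.

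A reader might infer more, and the document does not support it:
- That the analysis must favour relugolix or is uninformative. The difference can move either way.
- That women with incomplete collection are never counted as non-responders. Those whose measured volume fails a criterion always are, and the primary and Analysis 6 may add others.
- That the trial's conclusion is at risk by a stated number of points. Without the row's frequency no such number can be given.

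This is a low-cost improvement to the sensitivity analyses and does not fault the primary analysis.

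**What to change.** Keep the current Sensitivity Analysis 2 and label it the all-responder scenario. For the same row (FPRR < 100%, volume < 80 mL and at least a 50% reduction) add:

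- **(a)** all women in the row scored as non-responders in both arms;
- **(b)** the row scored as non-response on relugolix + E2/NETA and by observed volume (response) on placebo, which is the adverse bound on the difference.

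Report these beside the primary result, with the number of women in the row by arm. State that the scenarios are deliberately extreme, because a single missed product-day is enough to enter the row. State also whether the imputations for the other rows are held fixed across scenarios.

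The cost is one or two further runs of the existing Cochran-Mantel-Haenszel program. No new data are needed, and neither the primary analysis nor alpha changes. Scenario (b) cannot give a larger difference than the primary if the other imputations are held fixed.

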7.3.8. Subgroup Analyses

Subgroup analyses of the primary efficacy endpoint comparing the relugolix + E2/NETA group versus the placebo group will be performed to assess whether treatment effects are consistent across clinically important subgroups. The odds ratio and its 95% CI based on a logistic regression model will be displayed in a forest plot for each subgroup. The logistic regression model will include treatment group, Baseline MBL volume value and geographic region as covariates. Subgroups will include, but will not be limited to, the subgroups outlined in [Table 9](#).

Table 9: Planned Subgroup Analyses

Subgroup Name	Subgroup Level
Geographic region	North America vs Rest of World
Menstrual blood loss volume at Baseline (mL)	< 225 vs \geq 225 < 120, 120 to < 160, 160 to < 225, \geq 225
Age category (years)	< 40 vs \geq 40 < 35, 35 to < 40, 40 to < 45, \geq 45
Race	Black or African American vs Not Black or African American; Black or African American, White, Other
Volume of myoma at Baseline (cm ³)	< 25 vs \geq 25
Volume of uterus at Baseline (cm ³)	< 300 vs \geq 300
BMI (kg/m ²) at Baseline	< 30 vs \geq 30 < 25, 25 to < 30, 30 to < 35, 35 to < 40, \geq 40
Maximum NRS score for uterine fibroid-associated pain at Baseline	< 4 vs \geq 4
History of prior pregnancy	Yes/No

Abbreviations: BMI = body mass index; NRS = Numerical Rating Scale.

7.4. Secondary Efficacy Endpoints

Secondary efficacy variables include seven key secondary endpoints with alpha-protection and other secondary endpoints. All secondary efficacy endpoints and analyses are summarized in [Appendix 1](#).

The treatment effect of relugolix + E2/NETA (Group A) compared to placebo (Group C) will be tested for the alpha-protected secondary endpoints using a gate-keeping procedure (see [Section 7.4.1](#)).

Comparative statistics (p-values, 95% CIs for differences) will be provided for treatment comparison of the relugolix + E2/NETA group with the placebo group for all other secondary efficacy endpoints. Treatment difference between the relugolix + delayed E2/NETA group and the placebo group will be formally tested only for the primary efficacy endpoint. There will be no statistical testing for treatment differences between the relugolix groups (relugolix + E2/NETA group against relugolix + delayed E2/NETA group) for any efficacy endpoint (see [Section 7.4.2](#)).

[figure not shown]
7.4.1. Key Secondary Efficacy Endpoints with Alpha-Protection

For testing whether relugolix + E2/NETA (Group A) is statistically significantly superior to placebo (Group C) for the primary efficacy endpoint as well as the seven key secondary endpoints listed below, a gate-keeping mixed sequence testing procedure will be applied to maintain the family-wise type I error rate. Under this testing procedure, the primary endpoint

will be tested first at a 2-sided 0.05 significance level. If the p-value for primary endpoint is < 0.05 , the seven key endpoints listed below will be tested sequentially in the order depicted in [Figure 3](#).

For the relugolix + E2/NETA group to be considered statistically superior to the placebo group on a secondary endpoint, the two-sided p-value must be < 0.05 for that secondary endpoint and for all higher-ranking secondary endpoints, as well as for the primary endpoint. If the two-sided p-value is < 0.05 for the fourth endpoint (proportion of women with a hemoglobin ≤ 10.5 g/dL at Baseline who achieve an increase of > 2 g/dL from Baseline at Week 24), the remaining three endpoints (the fifth, sixth, or seventh) will be tested using the Hochberg step-up procedure.

Figure 3: Mixed Sequence Testing Procedure for Primary and Key Secondary Endpoints

Abbreviations: BPD = Bleeding and Pelvic Discomfort; EP = endpoint; Hgb = hemoglobin; max = maximum; MBL = menstrual blood loss; M-vol = myoma volume; NRS = Numerical Rating Scale; PE = primary endpoint; Prop = proportion; UFS-QoL BPD = Uterine Fibroid Symptom and Health-Related Quality of Life Bleeding and Pelvic Discomfort; U-vol = uterine volume.

From the Hochberg procedure, the p-values will be calculated for the three endpoints (5, 6, and 7) and ranked from the smallest to the largest. The endpoint corresponding to the largest p-value gets tested first. If the p-value is < 0.05 , then no further testing will occur, and it will be concluded that all three endpoints are positive. Otherwise, the endpoint corresponding to the second largest p-value will be tested. If the p-value is < 0.025 , then no further testing will occur, and it will be concluded that the endpoints corresponding to the middle and smallest p-values are positive. Otherwise, the endpoint with the smallest p-value will be tested. If the p-value is < 0.0167 , no further testing will occur, and it will be concluded that only the endpoint with the smallest p-value is positive. Otherwise, all three endpoints did not pass the statistical significance criterion at 0.05 level.

The seven key secondary efficacy endpoints are as follows:

1. Proportion of women who achieve amenorrhea over the last 35 days of treatment;
2. Percent change from Baseline to Week 24 in MBL volume;
3. *Change from Baseline to Week 24 in Bleeding and Pelvic Discomfort Scale score as measured by the UFS-QoL Symptom Severity Scale (Q1, Q2, Q5);*
4. *Proportion of women with a hemoglobin ≤ 10.5 g/dL at Baseline who achieve an increase of > 2 g/dL from Baseline at Week 24*
5. *Proportion of women who achieve a maximum NRS score ≤ 1 for uterine fibroid associated pain over the last 35 days of treatment in the subset of women with a maximum pain score ≥ 4 during the 35 days prior to randomization;*
6. Percent change from Baseline to Week 24 in uterine fibroid volume;
7. Percent change from Baseline to Week 24 in uterine volume.

For key secondary efficacy endpoints (1, 4, and 5) that are evaluating proportions, treatment comparisons will be performed using a stratified Cochran-Mantel-Haenszel test with the randomization stratification factors as strata. Point estimates and 2-sided 95% CIs for treatment differences in proportions will be provided.

For key secondary endpoint 4, an increase in hemoglobin of 2g/dL is considered clinically meaningful, because it corresponds to approximately the same increase as that expected after a transfusion of ~ 2 units of packed red blood cells (Man, 2016; Bachowski, 2017).

For deriving the key secondary endpoint 5 (proportion of women who achieve a maximum NRS score ≤ 1 for uterine fibroid-associated pain over the last 35 days of treatment in the subset of women with a maximum pain score ≥ 4 during the 35 days prior to randomization), the patient subset and Week 24/EOT maximum value are determined as follows.

Because patients were asked to begin eDiary entries after returning the first collection of feminine products, the number of eDiary entries made during screening varies with the duration of screening for each patient. Some patients required only one collection to be randomized, whereas others required as many as four collections to confirm eligibility.

Once the qualifying menstruation was completed and the patient qualified for randomization based upon resulting MBL volume(s), the recording of patient's NRS scores for screening phase

will be ended and the number of pain score days at Baseline can be as short as 7 days or as long as 70 days prior to randomization. If a patient meets the subset definition (maximum NRS score ≥ 4 at Baseline) over a portion of the screening days (eg, 7-70 days), she will also meet the subset definition on the entire 35 days interval.

Since the maximum NRS value is used to determine inclusion into the subset rather than an average NRS value, the variable number of days for inclusion of patients has no major impact on determining patient subset. To ensure robust estimate of response, the minimum number of non-missing daily pain scores required to calculate the maximum score at Week 24/EOT is at least 28 days (80% of the last 35 days of treatment) of pain scores recorded in the e-Diary entry.

The primary analysis of key secondary endpoint 5 will be analyzed for the subset of women who have a maximum pain score ≥ 4 during the 35 days prior to randomization and who have at least 28 days (80% of the last 35 days of treatment) of pain scores recorded in the e-Diary at Week 24/EOT. In addition, a sensitivity analysis will be conducted on the subset of women who have a maximum pain score ≥ 4 during the 35 days prior to randomization without restricting number of days of pain scores recorded in the e-Diary.

The analysis for endpoint 5 (proportion of women who achieve a maximum NRS score ≤ 1 for uterine fibroid-associated pain over the last 35 days of treatment in the subset of women with a maximum pain score ≥ 4 during the 35 days prior to randomization) will also be performed using NRS scores reported on eDiary during menstrual and non-menstrual days.

For key secondary efficacy endpoints (6 and 7) evaluating percent change from Baseline in uterine fibroid volume and uterine volume that are measured only at Week 24, an analysis of covariance (ANCOVA) model will be used to assess treatment effect with treatment, randomization stratification factors and Baseline value as covariates.

For key secondary efficacy endpoints (2 and 3) evaluating the change (absolute or % change) from Baseline to Week 24, treatment comparisons will be performed using a mixed model repeated measures approach with treatment, visit, randomization stratification factors and treatment by visit interactions included as fixed effects and random effects (from the individual patients). In this model, an unstructured variance-covariance matrix is assumed for each patient.

